11.0 Study Timelines

11.1 Describe the anticipated duration of the study needed to enroll all study subjects.

PROTOCOL TITLE:

Response: We anticipate that we will enroll all participants within a 3 month period and before the end of Fall semester.

11.2 Describe the duration of an individual subject's participation in the study. Include length of study visits, and overall study follow-up time.

Response: The maximum length of time a participant will be on the study is 6 weeks (see Figure 1 above). Subjects will commit approximately 30 minutes each morning to eat breakfast and collect the rest of the meals for the day. They will commit approximately 30-60 minutes on 3 occasions to deliver stool sample sand have blood drawn. After completing the study, no follow up will be needed.

11.3 Describe the estimated duration for the investigators to complete this study (i.e. all data is collected and all analyses have been completed).

Response: We anticipate that primary endpoints will be generated within 1 year of initiating subjects on the study.

12.0 Research Setting

12.1 Describe all facilities/sites/locations where you will be screening and conducting research procedures. Include a description of the security and privacy of the facilities (e.g. locked facility, limited access, privacy barriers). Facility, department, and type of room are relevant. Do not abbreviate facility names.

Example: "A classroom setting in the Department of Psychology equipped with a computer with relevant survey administration software," "The angiogram suite at Stony Brook University Hospital, a fully accredited tertiary care institution within New York State with badge access,"

Response: The in-person interview will be conducted in room 206 (private office) of the Earth and Space Science (ESS) building at Stony Brook University. Meals will be provided in a semi-private reserved area on the 2nd floor of the Student Activity Center. Stool samples will be delivered and blood samples taken at Student Health Services, a location already established to ensure confidentiality.

12.2 For research procedures being conducted, for this study, external to SBU and its affiliates (e.g., in schools, out-of-state, internationally, etc.) describe:

- *Site-specific regulations or customs affecting the research*
- *The composition and involvement of any community advisory board*
- *Local scientific and ethical review structure outside the organization.*

PROTOCOL TITLE:

- *Local issues affecting the research and rights of research subjects.*

NOTE: This question is not referring to multi-center research. If this research is being conducted internationally, Supplemental Form C must be completed and uploaded.

Response:

N/A: This study is not conducted outside of SBU or its affiliates.

13.0 Resources and Qualifications

13.1 The Principal Investigator (PI) must confirm, in consultation with Chair and Dean as applicable, that adequate resources are present to conduct and complete the study compliantly and safely. Specifically:

- NO** **YES** *The proposed subject population(s) are available in sufficient numbers to meet the study requirements*
- NO** **YES** *Sufficient funds are available to conduct and complete the study compliantly and safely*
- NO** **YES** *The PI and study team have sufficient time to conduct and complete the study compliantly and safely*
- NO** **YES** *The PI has determined that the named study team is qualified to conduct the research compliantly and to monitor the safety and welfare of the enrolled research subjects effectively.*
- NO** **YES** *The PI ensures that the study team is fully aware of his/her involvement in this study and the details of the study protocol*
- NO** **YES** *The PI ensures that the study teams will only be involved in research procedures for which they have been trained, and are currently certified and/or licensed, if required..*

13.2 Describe the availability of medical or psychological resources that subjects might need as a result of anticipated consequences of the human research, if applicable. (e.g, “on-call availability of a counselor or psychologist for a study that screens subjects for depression”).

Response: We don't anticipate any adverse events given the nature of this study, but subjects will have access to any medical care that is needed through Student Health Services.

13.3 Describe your process to ensure that all study team members are updated on the progress of the research and the regulatory requirements (including enrolled subjects, unanticipated problems etc.)

PROTOCOL TITLE:

Response: The study team will meet weekly to review the progress of recruitment, enrollment and sample collection. The PI will update the rest of the study team when data related to primary endpoints are generated.

14.0 Other Approvals

14. List approvals that will be obtained prior to commencing the research (e.g., University Hospital sign-offs per the UH Application, Cancer Center Scientific review, school, external site, funding agency, laboratory, Radiation Safety, IBC, SCRO, IACUC, RDRC).

Response:

N/A: This study does not require any other approvals.

15.0 Provisions to Protect the Privacy Interests of Subjects

15.1 Describe how you will protect subjects' privacy interests during the course of this research and any steps you will take to make the subject feel at ease.

NOTE: Privacy refers to an individual's desire/right to control access to or to place limits on whom they interact with or whom they provide personal information. Privacy applies to the person. Confidentiality refers to how data collected about individuals for the research will be protected by the researcher from release. Confidentiality applies to the data.

Examples of appropriate responses include: "participant only meets with a study coordinator in a private office setting where no one can overhear", or "the participant is reminded that they are free to refuse to answer any questions that they do not feel comfortable answering."

Response: In person screening will take place in a private office in which no one can overhear the discussion taking place. If they do not feel comfortable answering the health questionnaire they will be reminded that they do not have to. Meals will be provided in a semi-private area so participants don't feel uncomfortable receiving meals in an atypical manner. Blood will be drawn in a private room in a confidential manner.

16.0 Data Management and Analysis

16.1 Describe the data analysis plan, including any statistical procedures. This section applies to both quantitative and qualitative analysis.

PROTOCOL TITLE:

Response: For our primary endpoint of measuring circulating amino acid levels, data will be transformed to reflect log2 fold change values at each of the 2 time points following administration of the experimental diets, compared to the levels at baseline. Paired t-tests will be used to determine whether significant changes occur.

16.2 If applicable, provide a power analysis.

NOTE: This may not apply to certain types of studies, including chart/records reviews, survey studies, or observational studies. This question is asked to elicit whether the investigator has an adequate sample size to achieve the study objectives and justify a conclusion.

Response: The statistical analysis for the primary aim of the study will compare circulating amino acid levels in subjects after consuming high or low protein diets for 2 weeks. We will enroll 14 subjects with the prediction that 10 will complete the study. A sample size of 10 subjects will allow 80% power to detect minimum differences of 0.996 standard deviations in plasma amino acid levels at 5% significance with the use of paired t-tests.

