2.0 Scientific/Safety Endpoints

2.1 *Describe the scientific endpoint(s), the main result or occurrence under study.*

NOTE: Scientific endpoints are outcomes defined before the study begins to determine whether the objectives of the study have been met and to draw conclusions from the data. Include primary and secondary endpoints. Some example endpoints are: reduction of symptoms, improvement in quality of life, or survival. Your response should not be a date.

Response:

To determine whether reducing protein intake alters:

Circulating metabolites as determined by targeted metabolite profiling of blood.

Fecal metabolome as determined by targeted metabolite profiling.

Fecal microbiota as determined by 16S rRNA and metatranscriptomic analyses.

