5.0 Local Number of Subjects

5.1 *Indicate the total number of subjects who will be enrolled or records that will be reviewed through Stony Brook.*

Response: *We will enroll 14 subjects with the prediction that 10 will complete the study. Given that the subjects are healthy volunteers, medical records will not be searched but instead subjects' health status will be evaluated through a brief health questionnaire (provided as an attachment to this protocol application).*

5.2 *If this study is only being conducted through Stony Brook, provide statistical justification (i.e. power analysis) for the number of subjects provided in 5.1 above. If qualitative research, so state, and provide general justification for the total number of subjects proposed.*

Response: The statistical analysis for the primary aim of the study will compare circulating amino acid levels in subjects after consuming high or low protein diets for 2 weeks. We will

PROTOCOL TITLE:

enroll 14 subjects with the prediction that 10 will complete the study. A sample size of 10 subjects will allow 80% power to detect minimum differences of 0.996 standard deviations in plasma amino acid levels at 5% significance with the use of paired t-tests.

5.3 If applicable, indicate your screen failure rate, i.e., how many subjects you expect to screen to reach your target sample.

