19.0 Withdrawal of Subjects

N/A: This study is not enrolling subjects. This section does not apply.

19.1 Describe anticipated circumstances under which subjects may be withdrawn from the research without their consent.

Response: Subjects may be withdrawn from the study if they begin taking antibiotics or are diagnosed with a significant illness of the gastrointestinal tract while on the study. Additionally, if subjects fail to pick up their meals or eat the provided meals for more than 2 days in a row, they will be removed from the study.

19.2 Describe any procedures for orderly termination.

NOTE: Examples may include return of study drug, exit interview with clinician.

Include whether additional follow up is recommended for safety reasons for physical or emotional health.

Response: The subject will be contacted and informed of their removal from the study. No follow up will be needed.

19.3 Describe procedures that will be followed when subjects withdraw from the research, including retention of already collected data, and partial withdrawal from procedures with continued data collection, as applicable.

Response: If a subject is removed from the study before the second specimen collection, the specimens and dietary data from that individual will not be used for analysis. Already collected specimens will be destroyed. If a subject is removed from the study following the second

PROTOCOL TITLE:

specimen collection but before the last collection, the samples from the first 2 collections and dietary data collection up to withdrawal will still be analyzed.

19.4 Describe what will happen to data already collected.

Response: Data from specimen analyses will not be generated until all subjects have completed the study. If a subject is removed from the study following the second specimen collection but before the last collection, the samples from the first 2 collections will still be analyzed and dietary data collected up until that point will be analyzed.

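### The primary amino acid analysis names no lead amino acid, summary measure or multiplicity method, so the stated 5% and 80% describe a single test and not a set of tests

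*Combined protocol and SAP*

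**What the plan says.** Section 2.1 describes the blood endpoint as "Circulating metabolites as determined by targeted metabolite profiling of blood". Section 16.1 narrows this for analysis: "For our primary endpoint of measuring circulating amino acid levels", the data become "log2 fold change values at each of the 2 time points following administration of the experimental diets, compared to the levels at baseline", and then "Paired t-tests will be used to determine whether significant changes occur". Section 16.2, repeating 5.2, says the primary analysis will "compare circulating amino acid levels in subjects after consuming high or low protein diets for 2 weeks". It sizes the study on 10 completers for "80% power to detect minimum differences of 0.996 standard deviations in plasma amino acid levels at 5% significance with the use of paired t-tests".

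No section gives the number of amino acids, a lead amino acid, a total or other summary, or a familywise or false-discovery method. The side of the test and the kind of SD are also unstated.

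Three other places bear on the point:
- Section 10.1 lists blood metabolites, fecal microbiota and fecal metabolites all as primary endpoints.
- Section 19.3 keeps the first two collections from subjects removed before the third.
- Section 1.1 says positive data will supply the rationale for a study in cancer patients, without defining positive.

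**The concern.** A targeted panel normally returns several amino acids per sample, and 16.1 speaks of t-tests in the plural. The natural reading is one test per amino acid, each at 5%. The 5% error rate and 80% power then belong to each test and not to the conclusion drawn from all of them.

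The conclusion carries weight because it is the stated basis for moving to patients. If any single amino acid with p<0.05 counts as positive, a false positive is much more likely than 5%. If an adjustment or a summary is chosen after the data are seen, the stated power no longer describes the analysis and the choice itself is open to selection.

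**Working it through.** **Inputs from the documents.** n = 10 completers, significance 5%, power 80%, difference 0.996 SD (5.2, 16.2); paired t-tests (16.1).

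**Assumed, not in the documents.** m = 10 or 20 amino acids; equal correlation r between them of 0 to 0.9; normal within-subject differences in log2 level.

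**1. The plan's own figure.** For one two-sided paired t-test, power = P(|T| > t(0.975; 9 df)), where T is noncentral t with noncentrality 0.996 × √10 = 3.150 and the critical value is 2.262. The result is 0.800, so the stated figure reproduces. A one-sided test would give 89.5% and a normal approximation 88.3%. The plan's number is therefore the exact two-sided single-test figure, in units of the SD of the paired difference.

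**2. The contrast.** If the two fold changes in 16.1 are paired with each other, log2(low/baseline) − log2(high/baseline) = log2(low/high). Baseline cancels and 16.1 agrees with 16.2.

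**3. Error across the list, low versus high, no adjustment, no true change.** For independent tests the chance of at least one p<0.05 is 1 − 0.95^m: 40.1% for m = 10 and 64.2% for m = 20. Simulation (40,000 runs) gives:

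| m | r = 0 | r = 0.5 | r = 0.7 | r = 0.9 |
|---|---|---|---|---|
| 10 | 40.0% | 30.6% | 23.1% | 14.0% |
| 20 | 64.2% | 45.0% | 32.1% | 17.5% |

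The expected number of false positives is 0.05 × m, or 0.5 and 1.0, at any correlation. Counting only falls on the low protein diet, the chance is 7-40%, against 2.5% for one test.

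**4. Power once the list is adjusted.** Under Bonferroni, power per test at 0.996 SD is 37% (m = 10, level 0.005) or 27% (m = 20, level 0.0025). Under Benjamini-Hochberg at 5%, m = 20, average power over the truly changed amino acids (each by 0.996 SD) is:

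| r | 5 changed | 10 | 15 | 20 |
|---|---|---|---|---|
| 0 | 43% | 59% | 69% | 75% |
| 0.5 | 44% | 57% | 65% | 71% |

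**5. One summary instead.** For the mean log2(low/high) over 20 amino acids with equal SDs and k of them lowered by 0.996 SD, the standardised effect is 0.996 × (k/20) / √((1 + 19r)/20). At r = 0.5 the denominator is √0.525 = 0.725. For k = 5, 10, 15, 20 the effect is 0.344, 0.687, 1.031, 1.375 and power is 16%, 49%, 83%, 97%. At r = 0.9 power is 12%, 32%, 60%, 84%.

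**6. Would Benjamini-Hochberg support an 'at least one significant and lower' rule?** When nothing changes, a false 'lower' call occurs in about 1-3% of studies. When 5, 10 or 15 of 20 truly rise by 0.996 SD and none fall, it occurs in about 7-9% at r = 0, 3-4% at r = 0.5 and about 1.5% at r = 0.9. FDR control does not bound this rule's error.

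**The case against.** The text never says that each amino acid is tested separately or that any p<0.05 is a success. Circulating amino acid levels could mean a total, and the plural t-tests could refer to the two time points. The list size and correlations are assumptions, and independence, which gives the 64%, is an extreme for analytes from one blood sample. The study is small, self-controlled and rated minimal risk, and no treatment decision hangs on a p-value. Lowering as the hoped-for direction comes from the benefits statement in 21.2; the hypothesis in 1.2 has no direction.

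All of this stands as a limit on certainty: the omission is certain, the inflation conditional. It does not remove the point. No total is defined, even correlation 0.9 leaves 14%, and the plan itself sets a primary endpoint, a 5% level, 80% power and a link to a patient study.

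Three stronger readings are tempting and unsupported:
- A reader might infer that the power calculation is wrong. It reproduces exactly for one test.
- A reader might infer that 16.1 contradicts 16.2. It need not, because baseline cancels. Testing each diet against baseline is also possible, and keeping two-collection subjects under 19.3 lends that reading some weight. Only under it would the unadjusted chance be about 24-86% for 10-20 amino acids (9% for one).
- A reader might infer that the plan commits to calling any single hit positive. It leaves positive undefined.

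**Conclusion.** The point holds in conditional form. The primary analysis has no lead amino acid, summary or multiplicity method, and its power statement is right for one two-sided paired t-test only. On the natural, unwritten reading of unadjusted tests per amino acid, the chance of at least one false p<0.05 is about 14-64%, assuming 10-20 amino acids at correlation 0 to 0.9. The stated 5% and 80% then do not describe the set of tests. The design can stay; the claim rule should be written down.

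**What to change.** **Section 16.1.** Name log2(low/high) as the primary contrast, matching 16.2, and make diet-versus-baseline contrasts secondary. List the amino acids. For the single go-forward claim, use one prespecified summary, for example the mean log2(low/high) over the list, as the one two-sided 5% test. Report individual amino acids with Benjamini-Hochberg at 5% FDR as a list of findings. Do not use 'at least one significant and lower' as the success rule unless a familywise method such as Holm replaces it.

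**Sections 10.1 and 19.3.** State that circulating amino acids are the single primary endpoint, so that the three in 10.1 are reconciled with 16.1. State that subjects with only the first two collections contribute to high versus baseline only.

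**Sections 5.2 and 16.2.** Restate the figure as 80% power for 0.996 SD of the within-subject difference in log2 level, for a single two-sided 5% test. With a summary as the primary test, that SD is the summary's own.

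**Cost.** Wording, a short analysis program, and decisions on the list and summary; no extra subjects, samples or visits. The summary loses power when only part of the list moves, and opposing changes cancel (16% power with 5 of 20 lowered, 97% with all 20, at correlation 0.5). Average per-analyte power after Benjamini-Hochberg is about 43-75% in the assumed scenarios.

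**Timing.** Section 19.4 says "Data from specimen analyses will not be generated until all subjects have completed the study", so on that sequence the rule can be fixed before results exist. The documents do not show the study's current status.

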17.0 Confidentiality

A. Confidentiality/Security of Study Data

Describe the local procedures for maintenance of security and confidentiality of **study data and any records that will be reviewed for data collection.**

17.1 Where and how will all data and records be stored? Include information about: password protection, encryption, physical controls, authorization of access, certificates of confidentiality, and separation of identifiers and data, as applicable. Include physical (e.g. paper) and electronic files.

Response: Qualtrics uses "Transport Layer Security" encryption for all transmitted data, and is hosted by Stony Brook University Division of Information Technology for the purpose of conducting research. Subjects will enter their ID number on every survey and this will be data to be downloaded and organized by subject ID in an Excel spreadsheet. Electronic documents will be stored on a password-protected share drive and access to the drive will be limited to members of the study team. Paper records will be stored in a locked filing cabinet in the office suite of the Division of Nutrition. All documents will be de-identified and coded except for a master electronic document containing the key to the codes, which will be stored on a password-protected drive by the PI.

17.2 How long will the data be stored?

PROTOCOL TITLE:

Response: Data will be stored indefinitely to allow for endpoints to be assessed at a later time point.

17.3 Who will have access to the data?

Response: Members of the study team listed in "myResearch" proposal

17.4 Who is responsible for receipt or transmission of the data?

Response: Members of the study team listed on "myResearch" proposal

17.5 How will the data be transported/transmitted?

Response: Participant-generated data (i.e. responses to screening questions) will be submitted via Qualtrics. Data input or analysis carried out by members of the study team will be done on SBU tagged computers and files saved to the password-protected drive.

B. Confidentiality of Study Specimens

Describe the local procedures for maintenance of confidentiality of study specimens.

N/A: No specimens will be collected or analyzed in this research.
(Skip to Section 18.0)

17.6 Where and how will all specimens be stored? Include information about: physical controls, authorization of access, and labeling of specimens, as applicable.

Response: Tubes containing subject specimens will be de-identified by replacing the subjects' name with a numbered code. The tubes will be stored in a -80° C freezer located in room 9-166 in the BST.

17.7 How long will the specimens be stored?

Response: Indefinitely

17.8 Who will have access to the specimens?

Response: Members of the study team listed on "myResearch" proposal

17.9 Who is responsible for receipt or transmission of the specimens?

PROTOCOL TITLE:

Response: Members of the study team listed on "myResearch" proposal

17.10 How will the specimens be transported?

Response: Specimens will be picked up from Student health services and transported to the [name] lab by members of the study team listed on "myResearch" proposal.

18.0 Provisions to Monitor the Data to Ensure the Safety of Subjects

N/A: This study is not enrolling subjects OR is limited to records review procedures only OR is a minimal risk study

18.1 Describe the plan to evaluate the data periodically regarding both harms and benefits to determine whether subjects remain safe. The plan might include establishing a data safety monitoring committee and a plan for reporting data monitoring committee findings to the IRB and the sponsor.

Response: N/A

18.2 Describe what data are reviewed, including safety data, untoward events, and efficacy data.

Response: N/A

18.3 Describe any primary or secondary safety endpoints.

Response: N/A

18.4 Describe how the safety information will be collected (e.g., with case report forms, at study visits, by telephone calls with participants).

Response: N/A

18.5 Describe the frequency of safety data collection, including when safety data collection starts.

Response: N/A

18.6 Describe who will review the safety data.

Response: N/A

PROTOCOL TITLE:

18.7 Describe the frequency or periodicity of review of cumulative safety data.

Response: N/A

18.8 Describe the statistical tests for analyzing the safety data to determine whether harm is occurring.

Response: N/A

18.9 Describe any conditions that trigger an immediate suspension of the research.

Response: N/A

